### 3. OUTCOMES

- i. **PRIMARY OUTCOME MEASURE:** The primary efficacy outcome is the mesh to vagina attachment time using these two techniques. The timing of the mesh attachment interval was defined as beginning at the time of the initial needle or anchor being loaded on the needle driver or anchor device within the body of the patient and was introduced into the tissue of the vagina to attach the piece of mesh. As long as minimum amounts are met, here is no boundary to the amount of passes used or the amount of sutures applied. The security of the attachment of mesh will be ascertained by the attending surgeon's clinical reasoning. The time interval will end at the time the final suture is detached or anchor placed. A recording of the suture quantity utilized for each mesh attachment interval and the quantity of sutures placed in order to attach the mesh will be done. As this a time consuming component of sacrocolpopexy, a reduction in time using the anchor technique would be of considerable interest. This Mesh Attachment Interval will be recorded along with occurrence of supracervical hysterectomy as well as number of sutures or anchors placed, technical difficulties experiences, and mesh type on a de-identified document for each subject

1. **Validation of primary outcome (timing surgical procedures):** Measurement of time to complete a component of surgery has been validated in the surgical literature[16,25].
2. **Randomization/Blinding:** While intraoperative outcomes are not blinded, the examining postoperative visit provider will be blinded to group allocation. Group assignment will be performed by randomization as above.

ii. **SECONDARY OUTCOME MEASURE:** Our secondary efficacy objectives include: 1) VAS of the operating surgeon subjective technique satisfaction assessment 2) post-operative POPQ, mesh erosion anatomic assessment, palpable anchor assessment and 3) VAS of the vaginal walls general appearance. The latter two will be recorded by the provider who is blinded at 6 weeks and 6 months, who will perform POP-Q as well as the VAS assessment of the walls of the vagina's general appearance. Surgical failure of a patient is if the points on POP-Q, if  $B_p, B_a \geq 0$  cm, or  $C > - \frac{1}{2}$  TVL. The VAS will have four components, global satisfaction, apex, anterior wall, and posterior wall. The instructions for all four VAS will be as follows: "Please designate a "X" at the VAS that rates closest your sacrocolpopexy evaluation." The anterior compartment assessment at the VAS left side will say "the vaginal mesh at the ANTERIOR seems to lay level without folding or bunching." At the other VAS side the text will say "mesh at the vaginal ANTERIOR is completely folded and bunched." Comparable phrasing will be used on the for posterior and apical compartment VAS. For the global satisfaction VAS, the side on the left it will say "I will use this suture routinely; as it meets my needs for attachment of mesh" and text at the other VAS end will say "I do appreciate the results, I will not use this attachment technique in my practice;"

iii. **SAFETY AND TOXICITY MEASURES:** Safety will be assessed as several points throughout the study. During the admission for surgical care, safety measures and complications will be assessed. During the surgery and admission, complications, including but not limited to hemorrhage, bleeding, nerve injury, infection, urinary retention, bowel injury, bladder/urethral injury will be assessed. Post-operatively at the 6 week, and month visit (along with query of electronic medical record for additional ER and ambulatory visits) additional safety measures will be assessed. At the standardized postoperative visits mesh exposure and erosion will be assessed. In addition pain and reoperation for pain or mesh erosion and exposure will be assessed.

4. **MONITORING AND ETHICAL CONSIDERATIONS:** To safeguard complete, reliable and accurate data, the principal investigator will:
  - i. provide preliminary and follow up training to study coordinators and providers on research procedure, participant recruitment, and completion of outcome reports
  - ii. work with the IRB to obtain approval of the study and the informed consent document before the study can begin. A study role list will be created to include all qualified persons to whom the investigator may delegate study-related duties
  - iii. Periodically evaluate outcome reports for correctness and missing values as well as keep a research database for the same and to ensure compliance with the IRB

- iv. be continuously available to back the research staff by email, and telephone
- v. conduct quality review of the database
- vi. supervise that once entered, subject data will be accessed only for two purposes, analysis and validation/verification/auditing.

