### 1. OBJECTIVES

1. **PRIMARY OBJECTIVE:** To assess the effect of absorbable anchor compared to suturing for mesh attachment to vagina in robotic assisted sacrocolopexy on the length of surgery for this portion of the procedure.
2. **SECONDARY OBJECTIVES:**
  - i. To assess intraoperative and
  - ii. postoperative complication rates,
  - iii. Intraoperative 10 cm visual analog scale (VAS), to subjectively assess surgeon satisfaction with the technique
  - iv. post-operative Pelvic Organ Prolapse Quantification (POPQ) evaluation for anatomic failure and
  - v. a VAS of the vaginal walls overall appearance
2. **HYPOTHESES** For women undergoing sacrocolpopexy surgery at a large managed care organization:
  1. **PRIMARY HYPOTHESIS:** Attachment of the mesh to the vagina with absorbable anchors compared to standard treatment (suturing) will require 50% shorter surgical time for the mesh attachment portion of the procedure.
  2. **SECONDARY HYPOTHESIS:** Anchor suture staples compared to standard treatment will:
    - i. have similar rates of intra-operative and post-operative complications
    - ii. have similar rates of surgical failure
    - iii. not have different appearance on the VAS of the vaginal walls
    - iv. elicit higher reported satisfaction from surgeons
3. **BACKGROUND**
  1. **PELVIC ORGAN PROLAPSE:** Pelvic organ prolapse (POP) is the descent of one or more of four different anatomic structures: a) the uterus (cervix), b) the apex of the vagina (in those status post-hysterectomy) c) the anterior vaginal wall, or d) the posterior vaginal wall. It is caused by chronic intra-abdominal pressure on weakened pelvic organ supports. An estimated 41.1% of women aged 50-79 have some degree of prolapse on exam [1,2], while only 2.9-8% of all adult women report symptomatic prolapse symptoms [3-5]. Severity of POP is defined by the Pelvic Organ Prolapse Quantification (POPQ) system [6]. Risk factors include age, childbirth (especially vaginal and operative vaginal deliveries), white race, family history, constipation, obesity, smoking, and menopause. Symptoms can include a vaginal bulge, pressure, or discomfort.

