#### **4. OVERVIEW OF DESIGN**

1. **DESIGN DESCRIPTION;** This is a multi-site prospective, randomized, single-blind, 2 arms-parallel, clinical trial to evaluate the effect of absorbable anchor versus suturing of polypropylene mesh to the vaginas fibromuscular layer on the length of procedure for women undergoing SCP for POP. This effect will be studied using timing of the surgical procedure.
2. The study consists of a 1-year enrollment period concurrent with a 1-year single blinded period (the intraoperative data in which the patient is blinded to group assignment, but the surgeon/investigator is not), followed by a 6-month postoperative double blinded period (in which both the patient and surgeon/investigator).
3. During enrollment, patients who meet the inclusion and not the exclusion criteria and provide informed consent for participation will be assigned randomly to receive either absorbable anchor mesh fixation or suture mesh fixation.

Figure 1. Flowchart of study schema

4. **SCREENING PERIOD:** Subject will be screened for eligibility during a 1-year period that will include the preoperative office visit and preoperative unit visit. Office staff (research nurses, nurse practitioners, residents, fellows, attendings) will obtain written informed consent from participants as a part of enrollment. Standard physical exam measures (including POPQ) will be performed during the office visit. The suture allocation sealed envelope will be opened intra-operatively once it is certain the attachment of mesh will occur via a technique that is minimally invasive.
5. **STUDY PERIOD:** Study duration will be the 1 year concurrent period where surgeries are performed as well as the subsequent 6 months where postoperative visits occur. After randomization and surgery occurs subjects will follow up for a total of 6 months, with three visits, one at 6 weeks, one at 6 months. During these postoperative visits, a standard physical exam will be performed looking for signs of POP recurrence, mesh erosion, palpable suture, anchors, and other physical findings. The

patient will complete standardized questionnaires assessing pain, satisfaction and other quality of life indicators.

6. **STUDY POPULATION:** Women with POP, scheduled for minimally invasive SCP will be eligible for enrollment

i. **INCLUSION CRITERIA:** All patients must meet all the following inclusion criteria.

1. Age 21 or older

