available and all surgeons will be trained in the use of both techniques. The two groups will be mesh attachment with 0 non-barbed delayed absorbable suture or anchor suture using the Reliatack™ articulating reloadable fixation device (Medtronic). A minimum number of suture attachment points will be 4 on each side of the vagina. The average number for most cases is typically 6 to 8 per side. The same number minimum number of anchors will be required for the anchor arm. The remaining portion of the procedures will be the same for both arms. Intra-operative details will be tracked including number of sutures/anchors placed per side, inability to complete anchor placement or suture placement and alternative method if needed, and anchor or suture exposure full thickness in the vagina, and insertion of anchor/suture in rectum or bladder requiring removal. The type of suture will not be revealed in the operative procedure or heading but will be described in the description of procedure. Perioperative antibiotics will be administered per operating room protocol. Patients will all be prescribed vaginal estrogen after surgery.

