(anchor or mesh) including total, anterior, posterior, inability to use randomized technique, conversion to open or alternative technique, surgeon satisfaction with method.

- v. **IMMEDIATE POSTOPERATIVE:** Length of stay in hours, pain medication use will be assessed.
- vi. **POSTOPERATIVE CLINIC VISITS:** In addition to the preoperative visit, patients will have data collection intraoperatively and during postoperative visits at 6 weeks, and 6 months. We will mask patients to the type of attachment used until after their 6 month visit. A provider (not the who did the surgery) will do the postoperative POPQ measurements to ensure masking to the attachment technique used during surgery.
- vii. **SAFETY ASSESSMENTS:** Safety is assessed as a component of the intraoperative record as well as a review of 6 months of electronic medical record of unscheduled office or emergency room visits in addition to assessments at the 6 week and 6 month postoperative visit.

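### Does the start of the mesh-attachment clock, with no named analysis set, leave failed or converted attachments wrongly counted in the primary comparison?

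*Protocol*

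**What the plan says.** Protocol section 1 sets the primary objective as the effect of anchors against sutures "on the length of surgery for this portion of the procedure". Section 4.3 says that eligible, consenting women "will be assigned randomly to receive either absorbable anchor mesh fixation or suture mesh fixation", and section 4.4 has the envelope opened during the operation, once a minimally invasive attachment is certain.

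Section 5.3.i defines the interval. It names loading of the first needle or anchor as the beginning, then adds "within the body of the patient and was introduced into the tissue of the vagina to attach the piece of mesh". For the stop it says: "The time interval will end at the time the final suture is detached or anchor placed". It also says: "As long as minimum amounts are met, here is no boundary to the amount of passes used".

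Section 5.1 sets a minimum of 4 suture points on each side of the vagina and adds: "The same number minimum number of anchors will be required for the anchor arm". The same section has the team track "inability to complete anchor placement or suture placement and alternative method if needed", and section 5.2.iv tracks "inability to use randomized technique, conversion to open or alternative technique" along with total surgical time and sacrocolpopexy time.

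Protocol 6.3 and SAP 1.3 name a t-test or Mann-Whitney U test for continuous outcomes. Protocol 6.4 and SAP 1.4 give the sample size and a 30% allowance for drop-out. None of these sections names an analysis population or says what the allowance covers.

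**The concern.** The plan expects some women not to be completed with the technique they were allocated, and two of its rules seem not to fit them.

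The first is the clock. If both loading and tissue entry are needed, an anchor device abandoned before any anchor enters tissue never starts it. The first suture needle does. The woman stays in the anchor arm with a pure suturing time, and the failed attempt counts as zero. If such failures are commoner with anchors, the anchor saving is overstated even in an analysis by allocated arm.

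The second is the minimum. It is stated in anchors for the anchor arm, so a woman switched to sutures after two or three anchors cannot meet it, yet the stop rule still gives her a time. With no analysis set named and an unexplained 30% allowance, an analyst might set her aside. With 25 women per arm, a few such decisions could move the estimated reduction and, in some trials, the significance of the primary test.

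**Working it through.** **Plan's own figures.** Inputs from Protocol 6.4 and SAP 1.4: means 40 and 20 min, SD 20 in both arms, α = 0.05 (two-sided assumed), power 80%. The standardised difference is (40 − 20)/20 = 1. The t-based solution is 16.7, hence 17 per arm, with power 80.7%. Allowing for drop-out, 17/(1 − 0.30) = 24.3, hence 25 per arm, where power is 93.4%. Both stated sizes reproduce.

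**When the clock can miss time (section 5.3.i).**
- If loading starts the clock, no time on a loaded device is lost.
- If loading plus tissue entry starts it, only time before the first entry is lost.
- After first entry, on either reading, the stop rule covers the last suture or anchor and is not tied to the allocated technique. Time lost in a later switch is counted.

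**Size of the possible loss.** The documents give no failure rate or lost time, so these are assumptions: k = 1 to 3 anchor-arm failures among 25, each finished by 40 min of suturing, with m = 5 to 20 min lost before entry.
- Recorded anchor mean = 20 + (k/25) × 20
- Actual anchor mean = 20 + (k/25) × (20 + m)
- Overstatement of the saving = k × m/25

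| k | Recorded mean (min) | Actual mean, m = 5 to 20 (min) | Overstatement (min) |
|---|---|---|---|
| 1 | 20.8 | 21.0 to 21.6 | 0.2 to 0.8 |
| 2 | 21.6 | 22.0 to 23.2 | 0.4 to 1.6 |
| 3 | 22.4 | 23.0 to 24.8 | 0.6 to 2.4 |

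Against a suture mean of 40 min this is 0.5 to 6 percentage points. At the extreme, the saving would be recorded as 40 − 22.4 = 17.6 min when it was 40 − 24.8 = 15.2 min. If failures and lost minutes are equal in the two arms, the effect on the difference cancels.

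**Converted cases: counted or set aside.** Assume k anchor-arm conversions with mean time c of 40 or 60 min. Counted as allocated, the anchor mean is 20 + k(c − 20)/25. For k = 3 and c = 60 this is 24.8 min, a reduction of (40 − 24.8)/40 = 38%. Set aside, the assumed reduction stays at 50%. Simulation with 25 per arm, normal times, SD 20 and a Welch t-test gives:

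| k | Reduction, as allocated (c = 40 / 60) | Power, as allocated | Significance differs from setting aside |
|---|---|---|---|
| 1 | 48% / 46% | 91% / 87% | 3% / 6% of trials |
| 2 | 46% / 42% | 88% / 79% | 5% / 14% |
| 3 | 44% / 38% | 85% / 68% | 7% / 24% |

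Power with conversions set aside is 92 to 93%.

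**Dependence on the model.** A normal distribution with mean 20 and SD 20 puts Φ(−1) = 16% of anchor times below zero, which is impossible for a duration. With lognormal times of the same means and SDs, and the Mann-Whitney test that the plan also names, the worst cell (k = 3, c = 60) has as-allocated power of about 94%, and significance differs in about 5% of trials. The other cells differ in about 2% or fewer.

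**The minimum (sections 5.1 and 5.3.i).** In 5.3.i the phrase about minimum amounts qualifies the absence of an upper limit on passes. It is not stated as a condition for having a time or being analysed. Section 5.1 sets the minimum and then provides for failure to complete and an alternative method, so the exception is foreseen.

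**The case for a change.** The strongest case for a change is that surgeons know the allocation, so both the timing rule and the handling of switches are better settled before any data are seen. The primary outcome is measured in the same operation in which the envelope is opened. Later loss to follow-up therefore cannot remove it, and an undefined 30% allowance leaves room to set awkward cases aside. At the 17 per arm the plan would accept, 2 anchor-arm conversions at 40 min cut the as-allocated difference from 20 to 17.6 min and power from 81% to 68%. A clarification would cost a few sentences.

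Some of this stands. The start event can be read in two ways, and the analysis set is not written down. The rest is weaker:

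- The fall in power is what conversions do to a comparison by allocated arm. It is not produced by the missing sentence.
- The 30% has ordinary explanations. Consent is taken at preoperative visits and allocation happens in theatre, so women can be lost in between, and others can miss the 6-month visit.
- An obvious rewording, starting the clock when the allocated device is first loaded, would do harm. A woman whose allocated technique is never loaded would have no start time, whereas the present rule, which refers to the first needle or anchor of either kind, gives her one.

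**Conclusion.** The concern does not call for a change. The clock issue arises on one of two readings, and only for attempts abandoned before first tissue entry. Under assumed failure counts and lost minutes it is worth 0.2 to 2.4 min of a 20-min saving, which would not reverse the result. The top of that range supposes 20 min lost without one anchor entering tissue, as long as the whole anchor time the plan assumes, in 3 of 25 women, although all surgeons are to be trained in both techniques. Sacrocolpopexy time, technical difficulties and conversions are recorded, so such cases would be visible.

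The unnamed analysis set is a gap that analysts would fill sensibly. In a randomised comparison of two techniques, analysis by allocated arm is the default, and nothing in either document excludes or moves converted women. In most simulated trials, counting them or setting them aside leads to the same conclusion. The least favourable figures, 68% power and 24% disagreement, need three long conversions confined to the anchor arm together with normal times. With lognormal times and a Mann-Whitney test they become about 94% and 5%. All these sizes rest on assumed failure rates, since the documents give none.

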2. Diagnosis of POP, defined as the descent of one or more of four different anatomic structures, a)the uterus(cervix), b)the apex of the vagina (in those status post hysterectomy) c) the anterior vaginal wall, or d) the posterior vaginal wall. This is defined on exam as the POPQ points Ba, C, or Bp >0 cm beyond the hymen, uterine(cervix) descent into at least the lower half the vagina (defined as point c> -tv/2) or post hysterectomy vault into the lower 2/3 of the vagina.  
Bothersome bulge symptoms as indicated on question 3 of the Pelvic Floor Disorder Inventory (PFDI-20) form relating to 'sensation of bulging' or something 'falling out'
3. Desire surgical treatment for POP with SCP
4. Available for up to 6 months of follow up
5. Not pregnant or desiring future pregnancy
6. Written informed consent is obtained.

ii. **EXCLUSION CRITERIA;** Patients are ineligible for the study if:

1. Known adverse reaction to synthetic mesh, or complications including but not limited to erosion, fistula, or abscess.
2. Cervical intraepithelial neoplasia (CIN2, CIN3, or cancer)
3. Unresolved chronic pelvic pain
4. Prior abdominal or pelvic radiation
5. Contraindications to the surgical procedures including known horseshoe kidney, pelvic abscess or active diverticular abscess or diverticulitis

7. **METHODS OF RECRUITMENT AND MULTIPLE STRATEGY OF RETENTION:** There are many women in the target population. We will educate the health personnel (research nurses, nurse practitioners residents, fellows, attendings) in two sites of a large managed care organization Female Pelvic Medicine and Reconstructive Surgery (FPMRS) to recruit this population. Subject retention strategies will include a \$20 visa gift card given to the subject on completing the 6 month follow up appointment, as well as phone call reminders of those appointment.

5. **STUDY PROCEDURES**

1. **INTERVENTION:** On day of surgery eligible individuals are randomized to have either absorbable anchor or suture fixation of mesh (Figure 1). The patients and all postoperative study staff will be blinded to treatment assignment and surgical time measurements. A block stratification with a computer-generated randomization schedule will be performed.  
Equipment needed for both techniques will be stocked and readily

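### The global satisfaction VAS has a mixed right end and a left end that fits only the suture arm; a smaller point is that no scoring order protects the blinded wall VAS and POP-Q

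*Protocol*

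**What the plan says.** **Satisfaction.** Protocol 1 (secondary objective iii) describes an intraoperative 10 cm VAS of surgeon satisfaction, and Protocol 2 (secondary hypothesis iv) expects it to be higher with anchors. The schedule in 5.2.i gives surgeon and fellow satisfaction its own row, marked at surgery. Vaginal wall appearance has a separate row, marked at the two postoperative visits. Section 5.2.iv lists satisfaction among the intraoperative items.

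Section 5.3.ii first lists surgeon satisfaction as item 1 and gives only the other two items to the blinded provider. It then describes a single VAS with four components (global satisfaction, apex, anterior wall, posterior wall) under one shared instruction, and it fixes the end texts. For global satisfaction, the left end says the rater will routinely use this suture because it meets the need. The right end says the rater appreciates the results but will not use the technique.

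**Blinded examination.** The same section has the provider record "post-operative POPQ, mesh erosion anatomic assessment, palpable anchor assessment and 3) VAS of the vaginal walls general appearance" at 6 weeks and 6 months. Section 4.5 says the examination at these visits is "looking for signs of POP recurrence, mesh erosion, palpable suture, anchors, and other physical findings". Safeguards are stated:
- 5.1: "The patients and all postoperative study staff will be blinded to treatment assignment and surgical time measurements".
- 5.2.vi: "A provider (not the who did the surgery) will do the postoperative POPQ measurements to ensure masking", and "We will mask patients to the type of attachment used until after their 6 month visit".
- 5.3.i.2: "the examining postoperative visit provider will be blinded to group allocation".
- 5.4.i: the principal investigator will "provide preliminary and follow up training to study coordinators and providers on research procedure".

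Neither document sets the order of palpation and scoring or records whether the blind held.

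**The concern.** A visual analogue scale is interpretable only if its ends are opposites on one idea. Here a surgeon who likes the result but finds the device awkward matches the right end, while a surgeon who dislikes both result and technique has no end that fits. In the anchor arm the favourable end names something that was not used. Both faults bear on the between-arm comparison the hypothesis needs, and neither can be repaired in analysis once forms are completed.

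The examiner point is separate. What is sought by touch is what differs between the arms. If it is found before the wall VAS or POP-Q is scored, those two outcomes may be scored with the arm known. The hypotheses are that failure rates are similar and that wall appearance does not differ. The wall VAS is the more exposed because it is a judgement; failure is a threshold on centimetre measurements.

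**Working it through.** **1. Satisfaction item: the text side by side.**

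| Feature | Protocol 5.3.ii | Elsewhere in the protocol |
|---|---|---|
| Left end | favourable, but names a suture | one arm uses anchors (5.1) |
| Right end | approval of results plus refusal to use | hypothesis iv concerns satisfaction alone (2) |
| Rater | item 1 is the operating surgeon's; the four-part VAS names no separate rater for it | surgeon and fellow (1, 5.2.i) |
| Time | described straight after the 6-week and 6-month task | at surgery (1, 5.2.i, 5.2.iv) |

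The two end-text faults stand on the wording alone. The placement is a drafting conflict that the other sections settle.

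**2. The plan's own figure, for context.** Protocol 6.4 and SAP 1.4 give 17 per arm for a 20-minute difference with SD 20, 80% power and α = 0.05. The exact two-sided t-test has power 78.1% at 16 and 80.7% at 17, so 17 is reproduced. Allowing for 30% dropout, 17/0.70 = 24.3, rounded up to 25. Nothing here changes these figures; n = 17 and n = 25 are used below.

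**3. Wall VAS, effect of unmasking by touch.** The documents give no palpability rate and no SD for the wall VAS. Assumed for scale: 10–30% of one arm unmasked per visit, and a 0.2–0.5 SD shift in those patients.
- Patients unmasked: 0.10 to 0.30 × 17 = 1.7 to 5.1; × 25 = 2.5 to 7.5.
- Bias = share × shift: 0.10 × 0.2 = 0.02 SD; 0.30 × 0.5 = 0.15 SD.
- Chance of p < 0.05 with no true difference: two-sided t-test, noncentrality = bias × √(n/2), df = 2n − 2.

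| Bias | n = 17 | n = 25 |
|---|---|---|
| 0.02 SD | 5.0% | 5.1% |
| 0.15 SD | 7.1% | 8.2% |

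For the chance to reach 10%, the bias must be 0.231 SD (n = 17) or 0.188 SD (n = 25). At a 0.5 SD shift that means 0.231/0.5 = 46% or 0.188/0.5 = 38% of one arm unmasked.

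**4. Anatomic failure.** Start from 0 versus 0 and let k patients in one arm be wrongly called failures. Uncorrected chi-squared is then 2nk/(2n − k), and the two-sided Fisher p-value is 2·C(n,k)/C(2n,k).

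| Test | n = 17 | n = 25 |
|---|---|---|
| Chi-squared, k = 3 | 102/31 = 3.29, p = 0.070 | 150/47 = 3.19, p = 0.074 |
| Chi-squared, k = 4 | 136/30 = 4.53, p = 0.033 | 200/46 = 4.35, p = 0.037 |
| Fisher, smallest k with p < 0.05 | k = 5, p = 0.044 | k = 6, p = 0.022 |

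Protocol 6.3 names chi-squared for anatomic failure and also allows Fisher's test for categorical variables. With 4 events the expected count is 2 per arm, so Fisher is the safer guide.

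**The case against.** **On the satisfaction item.** The ends still contrast routine use with non-use, so the direction of the scale is clear. That stands, but direction is not enough: the right end still credits the results, and the left end still misnames the anchor arm's method. A reader might also infer that the blinded examiner is meant to rate satisfaction with a technique they must not know. The documents do not support that. Section 5.3.ii gives the blinded provider only the last two items, and the schedule already places satisfaction at surgery. The placement is mostly loose drafting.

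**On the examiner.** Several objections stand.
- The blinding rule and its safeguards are explicit, and the order of boxes may be set on the case report form, which is not among the documents.
- The calculation unmasks one arm only. Sutures may be felt too, and unmasking in both arms could offset or add. It also covers only spurious differences, although these hypotheses are of similarity.
- The documents do not say whether touch tells a suture from an anchor, or whether the wall VAS needs touch.
- Touch during POP-Q may reveal the arm anyway, so ordering cannot remove the problem.

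A reader might infer that the blind is broken and the secondary results unreliable. Nothing in the documents shows that. Nor is the operative note a further gap. Under 5.1, "The type of suture will not be revealed in the operative procedure or heading but will be described in the description of procedure", but the requirement that postoperative staff be blinded already implies that the examiner does not consult that description before scoring.

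**Conclusion.** The satisfaction VAS should not be used as written: one end mixes two ideas, the other does not fit one arm, and its placement in 5.3.ii needs reconciling with 1, 5.2.i and 5.2.iv. This conclusion rests on the wording and needs no assumption.

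The missing scoring order is a real but secondary gap. Its true size is unknown. The range in the working depends entirely on the assumed share and shift, with one arm unmasked, and it points to a small effect of palpation on secondary outcomes. The case for acting is that it costs little. Attachment time is unaffected by either part.

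**What to change.** **Satisfaction VAS (main change).**
- In 5.3.ii, limit the blinded examiner's VAS to apex, anterior wall and posterior wall.
- State there that the surgeon and fellow complete global satisfaction at surgery, as the schedule already has it.
- Give the item single-idea, arm-neutral opposite ends. For example, left: *This technique does what I need for fixing the mesh; I will use it routinely.* Right: *This technique does not do what I need for fixing the mesh; I will not use it.*

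**Examiner's form (secondary change).**
- Record the wall VAS and POP-Q before the specific check for palpable sutures or anchors.
- Add one tick box after scoring: did the examiner learn the technique before scoring, yes or no. It prevents nothing, but it lets the report state the share unmasked.

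**Cost.** Form wording, one extra item and a fixed order of steps within existing visits. No added staff, visits or procedures. The order reduces unmasking but cannot remove it.
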